6.2 Safety Variables

Safety will be assessed by evaluation of the following variables:

- Occurrence of DLTs (Phase 1 part only)
- Adverse events (AEs)

A treatment-emergent adverse event (TEAE) is defined as an AE observed after starting administration of the study drug. If the adverse event occurs on first administration date of the study drug and the onset check box is marked "Onset after first ASP2215 taken" or the onset check box is left blank, then the adverse event will be considered treatment emergent. If the adverse event occurs on first administration date of the study drug and the onset check box is marked "Onset before first ASP2215 taken", then the adverse event will not be considered treatment emergent. If a subject experience an event both before starting administration of the study drug and after starting administration of the study drug, the event will be considered as TEAE only if it has worsened in severity (i.e. it is reported with a new

start date). All adverse events collected that begin within 30 days after taking the last dose of the study drug will also be counted as TEAE, except for subjects that undergo HSCT without leaving the study and plan to resume ASP2215 treatment after HSCT. For these subjects, TEAE is defined as adverse events observed after starting administration of the study drug until the last dose before pre-HSCT visit plus 30 days, and adverse events that begin after resumption of ASP2215 and within 30 days after the last dose of ASP2215 will also be counted as TEAE. Any AEs with onset dates completely missing will be considered TEAEs in summaries. AEs with partially missing onset dates will be assumed TEAEs unless the available portion of the date indicates that the onset was strictly before start of study drug or 30 days after the last dose of study drug. Missing or partial AE onset date will be imputed per Section 7.11.1.

ASP2215-related TEAE is defined as any TEAE with at least possible relationship (possibly or probably related) to ASP2215 as assessed by the investigator or with missing assessment of the causal relationship

A regimen-related TEAE is defined as any TEAE with at least possible relationship (possibly or probably related) to study treatment as assessed by the investigator or with missing assessment of the causal relationship.

Serious adverse events (SAEs) include adverse events that are flagged as serious by the investigator on eCRF or upgraded by the Sponsor based on review of the Sponsor's list of Always Serious term.

- Laboratory parameters
- Vital signs
- 12-lead ECG: including QT assessment

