7.11 Handling of Missing Data, Outliers, Visit Windows, and Other Information

7.11.1 Missing Data

The detail of missing efficacy variable is in Section 6.1.

Missing or partial start and stop dates of adverse events and concomitant medication will be imputed using the following algorithm:

- Imputation rules for partial or missing stop dates:
 - If the month and year are present, then impute as the last day of that month.
 - If only the year is present, impute as December 31 of that year.
 - If the stop date is entirely missing, assume the event or medication is ongoing.
- Imputation rules for partial or missing start dates:

Start Date		Stop Date						missing
		Complete: yyyymmdd		Partial: yyyymm		Partial: yyyy		
		< 1 st dose	≥ 1 st dose	< 1 st dose yyyymm	≥ 1 st dose yyyymm	< 1 st dose yyyy	≥ 1 st dose yyyy	
Partial: yyyymm	= 1 st dose yyyymm	2	1	n/a	1	n/a	1	1
	≠ 1 st dose yyyymm		2	2	2	2	2	2
Partial: yyyy	= 1 st dose yyyy	3	1	3	1	n/a	1	1
	≠ 1 st dose yyyy		3		3	3	3	3
Missing		4	1	4	1	4	1	1

1 = Impute as the date of first dose; 2 = Impute as the first of the month; 3 = Impute as January 1 of the year; 4 = Impute as January 1 of the stop year

The imputed dates will be used to determine whether an AE is/is not treatment emergent. Listings of AEs and concomitant medications will present the actual partial dates; imputed dates will not be shown.

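### SAP 6.2 counts as treatment-emergent some AEs that stopped before first dose (onset missing, or known only to the first-dose month or year), while 7.11.1 excludes them

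*SAP*

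**What the plan says.** Section 6.2 opens with the base definition: "A treatment-emergent adverse event (TEAE) is defined as an AE observed after starting administration of the study drug". Its check-box rule for the day of first administration refers to ASP2215, so study drug here means ASP2215. Three further sentences deal with incomplete onset dates:

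- Completely missing: "Any AEs with onset dates completely missing will be considered TEAEs in summaries". No exception is given.
- Partially missing: "AEs with partially missing onset dates will be assumed TEAEs unless the available portion of the date indicates that the onset was strictly before start" (meaning the start of ASP2215). A second exception covers an onset 30 days after the last dose. The stop date plays no part.
- Cross-reference: "Missing or partial AE onset date will be imputed per Section 7.11.1".

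Section 7.11.1 imputes start dates from a table that crosses what is known of the start date with what is known of the stop date. The codes are 1 (date of first dose), 2 (first of the month), 3 (1 January of the year) and, for a missing start with a stop before first dose, "4 = Impute as January 1 of the stop year". The section then states: "The imputed dates will be used to determine whether an AE is/is not treatment emergent". Listings show the actual partial dates, not the imputed ones.

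**The concern.** Two sections each claim to settle whether an AE is treatment-emergent, and they use different information. Where the stop date falls before first dose, the recorded data already show that the event ended before treatment with study drug. Section 7.11.1 uses that fact and 6.2 does not. Two programmers who each follow one section faithfully would produce different TEAE tables, and the one following 6.2 would count events that cannot meet that section's own definition.

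The SAP shows that the situation can arise. The onset check box has an option for onset before the first ASP2215 dose, so such AEs are expected on the CRF. The definition of registration failure describes subjects who had chemotherapy but never ASP2215. The Phase 1 PK windows in 7.11.5 place cytarabine samples on Days 1 and 3 of induction and the first ASP2215 profile on Day 4. The SAP does not state when AE collection starts.

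**Working it through.** There is no stated figure to reproduce; the check compares two classification rules. Let D be the first dose, S the stop date with S before D, and I the imputed onset.

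**Cells of the 7.11.1 table with a stop before first dose where the sections disagree**

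| Onset known | Stop known | Code | Imputed onset I | 7.11.1 | 6.2 |
|---|---|---|---|---|---|
| Nothing | Full date | 4 | 1 January of stop year | Not TEAE | TEAE |
| Nothing | Year and month | 4 | 1 January of stop year | Not TEAE | TEAE |
| Nothing | Year | 4 | 1 January of stop year | Not TEAE | TEAE |
| First-dose month | Full date | 2 | First of that month | Not TEAE | TEAE |
| First-dose year | Full date | 3 | 1 January of that year | Not TEAE | TEAE |
| First-dose year | Year and month | 3 | 1 January of that year | Not TEAE | TEAE |

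**Why 7.11.1 always gives an onset before first dose here**

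- Code 4: 1 January of the stop year is never later than S, so I ≤ S < D. With a stop known only to month or year, that month or year is itself before the one of first dose, and the same ordering follows.
- Code 2: the event began in the first-dose month and stopped before D, so it also stopped in that month. The first of the month is no later than S, so I ≤ S < D.
- Code 3: the event began in the first-dose year and stopped before D, so it stopped in that year. 1 January is no later than S, so I ≤ S < D.

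An enumeration of code 4 with complete stop dates agrees. It took every first-dose date in 2019 to 2021 (assumed years, 365 + 366 + 365 = 1,096 days) and stop dates 1 to 60 days earlier. Of 1,096 × 60 = 65,760 combinations, none gave an onset on or after first dose.

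**Why 6.2 gives TEAE.** A completely missing onset is a TEAE by the unconditional sentence. A partial onset equal to the first-dose month or year is not strictly before the start of study drug on its visible part, so the exception does not apply.

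**Where the sections agree.** For a completely missing onset with a stop on or after first dose, or with no stop date, code 1 imputes the first-dose date and both sections say TEAE. The exception would be a check box marked as onset before ASP2215, which is unlikely when the onset date is missing.

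**Meaning of first dose.** The table does not say whether this is ASP2215 or chemotherapy. An event that stopped before the first chemotherapy dose also stopped before a later first ASP2215 dose, so the conflict for completely missing onsets stands on either reading. If chemotherapy were meant, code 1 would impute an onset before ASP2215 wherever ASP2215 starts later, and the conflict would widen.

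**Size.** Denominators are the planned numbers in Section 4.1.1.

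- Phase 2: 1/80 = 1.25 percentage points.
- Phase 1 overall: 1/6 = 16.7 points.
- One Phase 1 part with 3 subjects: 1/3 = 33.3 points.

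These are ceilings per affected subject. Section 7.5.2 counts a subject once per preferred term and once per body system, so a subject with another TEAE in the same row moves nothing.

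**The case against.** The best defence is that 6.2 itself sends missing and partial onsets to 7.11.1, where the imputed date decides. On that reading the sentence on completely missing onsets is only the conservative default that code 1 carries out, and a programmer following the cross-reference would exclude an AE that ended before first dose. This softens the conflict but does not remove it. The sentence is unconditional, nothing says that 7.11.1 takes precedence over it, and the partial-onset sentence has its own test that ignores the stop date. Confining the 6.2 rule to summaries does not separate the two either, because 7.11.1 applies its imputed dates to TEAE status itself. A conservative default is reasonable when timing is unknown; here the stop date settles it.

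Two other objections stand. An AE whose onset is wholly unknown but whose stop is known to precede first dose should be uncommon, and no frequency can be derived from the SAP. Following 6.2 also errs only towards over-counting.

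A reader might infer that the sections clash for every AE with an incomplete onset date. They do not: the disagreement set out here is confined to the six cells above.

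**Conclusion.** The inconsistency is real but narrow. For AEs that stopped before first dose, with onset completely missing or known only to the first-dose month or year, 6.2 and 7.11.1 give opposite TEAE status, and the 6.2 result contradicts that section's own definition. It is a minor point. Efficacy analyses and the decision rule on the CR rate are untouched.

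The size rests on the planned 80 subjects in Phase 2: at most about 1.25 points in any one incidence per affected subject, with larger steps in the small Phase 1 tables. It would be tempting to read 1.25 points as what each such AE adds. The document does not support that, because subjects are counted once per term, the safety set may differ from 80, and Phase 1 and pooled tables have other denominators. Nor does it support a claim that the TEAE tables as a whole would be materially distorted, since the number of affected AEs is unknown and probably small.

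**What to change.** Replace both the completely-missing and the partial-onset sentences in 6.2 with one sentence:

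> AEs with completely or partially missing onset dates are considered TEAEs unless the available portion of the onset date, or the (complete or partial) stop date, shows that the event started or ended before the first dose of ASP2215, or the available portion of the onset date shows onset more than 30 days after the last dose of study drug; TEAE status follows the dates imputed in Section 7.11.1.

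Replacing both sentences matters. Deleting only the unconditional one would leave the partial-onset rule blind to the stop date, and a replacement without the last clause would lose the existing limit after last dose. The separate rule in 6.2 for subjects with on-study HSCT stays as it is.

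In the 7.11.1 table, define first dose, for AEs, as the first dose of ASP2215.

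The cost is one sentence and one table note. No imputation code changes and no new data are needed.

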6.3 Pharmacokinetic Variables

- Plasma concentration of ASP2215 and Cytarabine
- Pharmacokinetic parameters of ASP2215

6.4 Pharmacodynamic Variables

[Phase 1 part]

- Total FLT3 concentration
- Total AXL concentration

[Phase 2 part]

Not applicable.

6.5 Other Variables

- FLT3-ITD mutation status
- FLT3-TKD mutation status
- FLT3 mutation status

Either of FLT3-ITD mutation status or FLT3-TKD mutation status is positive, this variable shows positive.

- MRD

MRD negative is defined as summed FLT3-ITD signal ratio of any post-baseline sample $\leq 10^{-4}$. MRD positive is defined as summed FLT3-ITD signal ratio of any post-baseline sample $> 10^{-4}$.

- MR
MR is defined as summed FLT3-ITD signal ratio of any post-baseline sample $\leq 10^{-2}$.
No MR is defined as summed FLT3-ITD signal ratio of any post-baseline sample $> 10^{-2}$.
- FLT3-ITD signal ratio
FLT3-ITD signal ratio is defined as the ratio of FLT3-ITD sequence reads divided by the total number of FLT3 sequence reads. This is being calculated by central laboratory. For subjects with more than one FLT3-ITD variant, the FLT3-ITD signal ratio will be summed at each timepoint.
- Duration of exposure (days)
Duration of exposure to each treatment will be calculated in days, using the following formula:
 - Duration of exposure for each treatment cycle is defined as Last dose date – First dose date + 1 – (on-study HSCT period for subjects undergo on-study HSCT) for each cycle. For Phase1 part, last dose date of study drug exposure = (initial dose date of the cycle + 14 – 1) if last dose date of the cycle is not captured on dosing CRF.
 - Duration of exposure for each treatment period is calculated as sum of the duration of exposure for each treatment cycle.
 - Duration of exposure during study for study drug =
(Duration of exposure for Induction period) + (Duration of exposure for Consolidation period) + (Duration of exposure for Maintenance period).When the last date of exposure is beyond cutoff date, the cutoff date will be used as the last date of exposure. When the start or stop date is missing, then the exposure will be treated as missing.
- Number of dosing days (days)
Defined as number of days with non-zero dosing.
Number of dosing days is calculated for each treatment period.
- Cumulative dose (mg or g)
Defined as total amount of drug given to a patient, which calculated as follows:
 - ASP2215: Sum of (actual dose level * number of dosing days within each dose level)
 - Chemotherapy: Sum of actual dose across the days when administered.
Actual dose is calculated as:
(Actual volume administered / Total volume prepared)* Intended dose * Body surface area.

If number of doses taken is unknown, it will be treated as missing.

Cumulative dose is calculated for each treatment period.

- Average of daily dose (mg/day or g/day)

Defined as cumulative dose divided by number of dosing days.

Average of daily dose is calculated for each treatment period.

- Dose intensity (mg/day or g/day)

Represents unit of dose given to a patient per unit of time, calculated as cumulative dose divided by duration of exposure.

Dose intensity is calculated for each treatment period.

- Relative dose intensity (%)

Defined as dose intensity divided by planned dose intensity * 100%.

Relative dose intensity is calculated for each treatment period.

Where planned dose intensity (mg/day or g/day) will be calculated as follows:

- ASP2215: 120 mg
- Cytarabine, Induction for Phase 1 part: Calculated Dose in mg on CRF
- Cytarabine, Induction for Phase 2 part: $100 \text{ mg/m}^2 * \text{BSA}$
- Cytarabine, Consolidation for Phase 1 part: Calculated Dose (sum of Infusion 1 and 2) in g on CRF
- Cytarabine, Consolidation for Phase 2 part: $1.5 \text{ g/m}^2 * \text{BSA} * 2 \text{ times}$
- Idarubicin for Phase 1 part: Calculated Dose in mg on CRF
- Idarubicin for Phase 2 part: $12 \text{ mg/m}^2 * \text{BSA}$

Average of BSA and Calculated Dose across the days when administered will be used in the calculation of planned dose intensity.

- Previous and concomitant medication

The period of evaluation for previous medications is as follows:

- 28 days before Day 1 of induction period – before Day 1 of induction period.

Concomitant medication is defined as medication used between Day 1 of induction period and the last dose of treatment. For subjects who undergo HSCT without leaving the study and plan to resume ASP2215 treatment after HSCT, concomitant medication is defined as medication with at least one dose taken between Day1 of induction period and the start of the HSCT conditioning regimen, or between resumption of ASP2215 and the last dose of the study drug.

- Previous and concomitant transfusion

Previous transfusion is defined as transfusion received before Day 1 of induction period, i.e. transfusion completed before Day 1 of induction period.

Concomitant transfusion is defined as transfusion received between Day 1 of induction period and the last dose of treatment. For subjects who undergo HSCT without leaving the study and plan to resume ASP2215 treatment after HSCT, concomitant transfusion is defined as transfusion received between Day 1 of induction period and the start of the HSCT conditioning regimen, or between resumption of ASP2215 and the last dose of the study drug.

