5.6 MRD Analysis Set (MAS)

[Phase 1 part]

Not applicable.

[Phase 2 part]

Subjects who received at least one dose of study drug, were centrally confirmed as FLT3-ITD positive at screening and had a baseline and at least one post-baseline sample with MRD data.

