6.1.3 Secondary Efficacy Endpoints

[Phase 1 part]

Not applicable.

[Phase 2 part]

- Overall survival (OS)

OS is defined as the time from start date of the first treatment until the date of death due to any cause. For a subject who is not known to have died by the end of long-term follow-up, OS is censored at the date of last known alive.

As a sensitivity analysis, OS is defined similarly as the above, however, subjects who undergo HSCT will be censored at the time of HSCT.

- Event free survival (EFS)

The time from the date of start date of the first treatment until the date of documented relapse after CR, treatment failure or death from any cause, whichever occurs first. For a subject with none of these events, EFS is censored at the date of last disease assessment. Subject without post-treatment disease assessment will be censored at the start date of the treatment.

Treatment failure includes those subjects who failed to achieve CRc by the end of consolidation period, or who discontinued the treatment due to “lack of efficacy” without a previous response.

Treatment failure date refers to the end of treatment date for subjects with treatment failure.

- Relapse free survival (RFS)

The time from the date of achievement of first CRc until relapse or death from any cause, whichever comes first for subjects who achieve CRc. For a subject who is not known to have relapsed or died, RFS is censored on the date of last relapse-free disease assessment date.

Last relapse-free disease assessment date refers to the subject’s last disease assessment date.

- CR rate after each treatment therapy

Defined as the number of subjects who achieve the best response of CR divided by the number of subjects in the analysis population after each treatment therapy period.

Subjects with unknown or missing response, or who provide no information on response will be treated as non-responders and will be included in the denominator when calculating rates.

- CR rate without MRD after each treatment therapy

Defined similarly as CR rate after each treatment therapy. Responders achieve that the best response is CR and MRD status is negative. CRc rate without MRD after each treatment therapy will also be defined similarly.

- CRh rate after each treatment therapy

Defined similarly as CR rate after each treatment therapy.

- CRc (Composite CR) rate after each treatment therapy

CRc: CR + CRp + CRi

Defined similarly as CR rate after each treatment therapy.

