Defined as the time from the date of start date of the treatment until the date of having a neutrophil count of $\geq 1,000/\text{mm}^3$ and platelet count of $\geq 100,000/\text{mm}^3$. Subjects with none of these events are censored at the date of last assessment within each treatment cycle.

- MRD

MRD is defined as binary endpoint, negative or positive. More detail of the definition is in Section 6.5. MRD rate is defined as the percentage of subjects whose MRD is negative.

- MR

MR is defined as binary endpoint, MR or no MR. More detail of the definition is in Section 6.5. MR rate is defined as the percentage of subjects who achieve MR.

- MRD-negative CR rate after induction

Defined as the number of subjects who achieve the best response of CR and whose MRD is negative during induction period divided by the number of subjects in the analysis population during induction therapy period. Subjects with unknown or missing response, or who provide no information on response will be treated as non-responders and will be included in the denominator when calculating rates.

- Overall MRD-negative CR rate for any treatment period

Defined as the number of subjects who achieve the best response of CR and at least one post-baseline MRD is negative divided by the number of subjects in the analysis population. If subjects have multiple MRD samples collected across different timepoints, the overall MRD status is negative if there is at least one MRD sample is negative and the overall MRD status is positive if all available MRD samples are positive. Subjects with unknown or missing post-baseline MRD status, or who provide no information on post-baseline MRD status will be treated as MRD positive and will be included in the denominator when calculating rates.

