7.4 Analysis of Efficacy

[Phase 1 part]

The efficacy analysis will be performed on the FAS.

For response variables, best response after each treatment therapy period will be summarized. The number and percentage of subjects in each category will be presented together with two-sided exact 95% CIs based on binomial distribution. Swimmer's plot will be presented for response variables.

For time-to-event variables efficacy analysis will be summarized using descriptive statistics. The survival curve and the median will be estimated using the Kaplan-Meier method and will be reported along with the corresponding 95% CIs.

[Phase 2 part]

The efficacy analysis will be performed on the FAS and TTE-FAS. The interpretation of statistical results will be based on the FAS. The TTE-FAS will be used to analyze OS and EFS. Analysis of MRD and MR will be performed using MAS.

Primary efficacy variable

For primary efficacy variable, CR rate after induction therapy period, the two-sided 90% exact CI by Clopper-Pearson method will be calculated. The lower limit will be used to compare with the benchmark of CR rate of 55%. The number and percentage of subjects in each category and swimmer's plot will also be presented. As a supportive analysis, CR rate after induction therapy period reported by Day 60 and CR rate after induction therapy period not being dependent on RBC and platelet transfusion (No Transfusion of RBC and Platelet within 1 week prior to disease assessment) will also be calculated.

Other efficacy variables

For other efficacy variables, analysis method will be described as follows:

Categorical variables:

The number and percentage of subjects in each category will be presented together with two-sided exact 95% CIs based on binomial distribution. Swimmer's plot will be presented for response variables.

For response assessment variables, best response rate after each treatment therapy will be summarized. The number and percentage of subjects in each category will be presented together with two-sided exact 95% CIs based on binomial distribution. For subjects who undergo HSCT, any response assessment data after HSCT will not be used (i.e. for those subjects, only response assessment data before HSCT will be used).

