As a sensitivity analysis, response assessment will be defined similarly as the above analysis, however, all response assessment data will be used even if there were subjects who undergo HSCT (i.e. response assessment data after HSCT will also be used).

Time-to-event variables:

For time-to-event variables efficacy analysis will be summarized using descriptive statistics. The survival curve and the median will be estimated using the Kaplan-Meier method and will be reported along with the corresponding 95% CIs. Kaplan-Meier plot will be presented.

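### The Overall MRD-negative CR rate, and the MRD and MR rates, can count samples taken after HSCT, although the main response analysis stops at HSCT

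*SAP*

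**What the plan says.** **Response.** For Phase 2 response assessment variables, SAP Section 7.4 says: "For subjects who undergo HSCT, any response assessment data after HSCT will not be used". A sensitivity analysis reverses this: "all response assessment data will be used even if there were subjects who undergo HSCT".

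**MRD and MR.** Section 6.5 gives the sample rules: "MRD negative is defined as summed FLT3-ITD signal ratio of any post-baseline sample" at or below 10⁻⁴, and "MR is defined as summed FLT3-ITD signal ratio of any post-baseline sample" at or below 10⁻². Section 6.1.4 adds that "MRD rate is defined as the percentage of subjects whose MRD is negative". For the Overall MRD-negative CR rate, where a subject has several samples, "the overall MRD status is negative if there is at least one MRD sample is negative". Missing MRD status counts as positive and stays in the denominator.

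**Analysis set.** Section 7.4 assigns MRD and MR to the MAS. Section 5.6 requires that the subject "had a baseline and at least one post-baseline sample with MRD data". It sets no condition on HSCT.

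**Secondary endpoints.** For the CR rate without MRD, Section 6.1.3 says: "Responders achieve that the best response is CR and MRD status is negative". The CRc version follows the same pattern.

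**HSCT on study.** Sections 6.2 and 6.5 carry special rules (adverse events, exposure, concomitant medication, transfusion) for subjects who have HSCT while on study, including those who plan to resume ASP2215 afterwards.

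**The concern.** The SAP treats HSCT as a dividing line for morphologic response but states no such line for molecular data. Followed literally, the two halves of one composite have different data cut-offs: the CR half ends at HSCT and the MRD half does not.

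Molecular clearance that first appears after transplant could then be counted in a rate reported for the ASP2215 regimen. The trial has a single arm, so no comparison would show how much of the rate arose after transplant. The MRD results would also not line up with the morphologic rates reported beside them.

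**Working it through.** The SAP states no expected MRD or MR rate, so there is no planned figure to reproduce. The check is mainly a comparison of the rules.

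**Step 1. Cut-off by endpoint (Phase 2)**

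| Endpoint | Status | Limit on the CR part | Limit on the MRD or MR part |
|---|---|---|---|
| CR after induction (6.1.2) | primary | induction period | no MRD part |
| CR and CRc without MRD (6.1.3) | secondary | HSCT (7.4) | not stated; arguably HSCT |
| MRD rate, MR rate (6.1.4, 6.5) | exploratory | no CR part | none stated |
| MRD-negative CR after induction (6.1.4) | exploratory | induction period | induction period |
| Overall MRD-negative CR (6.1.4) | exploratory | HSCT (7.4) | none stated; one negative sample suffices |

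**Step 2. A subject who shows the mismatch.** The subject reaches CR and is MRD positive on every sample before HSCT. The subject stays on study through HSCT and has a negative sample afterwards. The CR was reached before HSCT, so it counts. The later sample is post-baseline, so one negative sample exists. The subject is an overall MRD-negative CR, although no sample before HSCT was negative.

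**Step 3. Direction for the Overall MRD-negative CR rate.** Let N be the denominator. It is fixed, because subjects with missing MRD status stay in it as positive. Let A be the number with CR before HSCT and at least one negative sample before HSCT. Let B be the number with CR before HSCT whose only negative samples come after HSCT.

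- Samples before HSCT only: A/N
- All samples: (A + B)/N
- Difference: B/N, which is zero or positive

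For the MRD and MR rates the direction is not fixed. The SAP does not say how several samples combine for these rates. In the MAS, a subject admitted only by a positive sample after HSCT adds one to the denominator and nothing to the numerator.

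**Step 4. Possible size, on assumed inputs only.** The SAP gives no transplant, sampling or clearance rate. Assume:

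- h, share transplanted: 0.2 to 0.6
- s, share of those sampled after HSCT: 0.5 to 1, or 0 if there is no such sampling
- q, MRD-negative rate before HSCT: 0.3 to 0.5
- c, clearance after HSCT among those still positive: 0.3 to 0.6

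If transplant and later sampling are unrelated to MRD status before HSCT, the rise in the MRD-negative rate is h × s × (1 − q) × c.

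- No sampling after HSCT (s = 0): 0
- Low end: 0.2 × 0.5 × 0.5 × 0.3 = 0.015, or 1.5 points
- Middle: 0.4 × 1 × 0.5 × 0.6 = 0.12, so 50% becomes 62%
- High end: 0.6 × 1 × 0.7 × 0.6 = 0.252, or about 25 points

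For the composite, these subjects must also have been in CR before HSCT, so on the same inputs the rise is at most this large.

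**The case against.** The strongest reply is that the Section 7.4 rule may already cover MRD. The section does not limit response assessment data to morphology, and the abbreviation list expands MR as molecular response. The secondary CR rate without MRD is defined by analogy with the CR rate after each therapy, which is under the cut. This stands in part: for the secondary CR and CRc rates without MRD, the fault is ambiguity rather than a clear omission. It is weaker for MRD and MR. Section 6.1.1 builds antitumor response from marrow findings, peripheral blasts, neutrophils and platelets, while Section 6.5 defines MRD and MR separately, from a central-laboratory sequencing ratio, and they have their own analysis set.

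Second, the Section 6.5 wording, with mirror-image rules for negative and positive, reads mainly as a way to classify each sample, not as a collection window. That is fair. The rule that one negative sample is enough appears only for the Overall MRD-negative CR rate.

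Third, the SAP does not cut everything at HSCT. Main OS is not censored there, EFS and RFS have no HSCT rule, and the duration endpoints censor only subjects who leave the study for HSCT. ASP2215 may resume after transplant, so an all-period rate could reasonably include that phase. This supports keeping an all-samples analysis. It does not justify different cut-offs within one composite.

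A reader might infer that transplant clearance is in fact credited to ASP2215 across all MRD endpoints, and always upward. The SAP does not show that. The MRD sampling schedule is not given there, MRD-negative CR after induction is confined to induction, and the direction is fixed for one endpoint only. Nor does the SAP give a reason for the Section 7.4 cut. An argument from the anti-leukaemic effect of transplant is inference, and the mismatch stands without it.

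**Conclusion.** The point holds in a limited form. The Overall MRD-negative CR rate can combine a CR from before HSCT with a negative MRD sample from after it, and the exploratory MRD and MR rates can include samples taken after HSCT. The secondary CR and CRc rates without MRD may or may not be protected by Section 7.4; the text does not settle it.

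For the Overall MRD-negative CR rate any effect is upward. This rests on its one-negative-sample rule and on keeping subjects with missing MRD status in the denominator. The effect arises only if MRD samples are taken after HSCT. The illustrative range shows what is possible and is not an estimate for this trial. The primary CR analysis and its 55% benchmark are unaffected, and MRD-negative CR after induction is largely unaffected. The gap should be closed because a stated rule, not just missing detail, allows the mixed count.

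**What to change.** State in Sections 6.5 and 7.4 that the main analyses of MRD, MR, CR and CRc without MRD, and Overall MRD-negative CR use only samples taken before HSCT. Use the cut that Section 7.4 already applies to response, which is HSCT itself. Section 6.5 uses the start of conditioning only for concomitant medication and transfusion, and adopting it here would create a new mismatch with the CR part. Present the all-samples version as a sensitivity analysis, parallel to the one for response. The same text should say whether a subject whose only post-baseline MRD sample follows HSCT remains in the MAS.

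The cost is about one sentence and one programming flag. The HSCT date is already needed for the OS sensitivity analysis, the duration endpoints and the response cut. The downside is a possibly lower MRD-negative rate in the main analysis.
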